11.4.6 Analysis of immunogenicity variables

At each sample time, the result of the ADA assay will be categorized as either positive or negative, and in the case of a positive result will be further characterized as either neutralizing or non-neutralizing.

ADA-positive patient is defined as a patient with at least 1 treatment-emergent or treatment-boosted ADA-positive sample during the TEAE period, where

- Treatment-emergent ADA-positive patient is defined as a patient with non-positive assay (meaning negative or missing) response at baseline but with a positive assay response during the TEAE period
- Treatment-boosted ADA-positive patient is defined as a patient with a positive ADA assay response at baseline and with at least a 4-fold increase in titer compared to baseline during the TEAE period.

ADA-negative patient is defined as a patient without a treatment-emergent or treatment-boosted ADA-positive sample during the TEAE period.

ADA prevalence and titer

The following summary will be provided based on the ADA population:

- Number (%) of patients with an ADA-positive sample at baseline
 - Number (%) of neutralizing antibody
 - Number (%) of non-neutralizing antibody
 - The summary statistics (including number, median, Q1, Q3, minimum, and maximum) of the titer for the baseline ADA-positive patients
- Number (%) of patients with an ADA-negative sample at baseline.

ADA incidence and titer

The following summary will be provided based on the ADA population during the TEAE period:

- Number (%) of ADA-negative patients
- Number (%) of ADA-positive patients
 - Number (%) of patients with neutralizing antibody
 - Number (%) of patients with non-neutralizing antibody
- Number (%) of treatment-emergent ADA-positive patients
 - The summary statistics (including number, median, Q1, Q3, minimum, and maximum) of the peak post baseline titer for treatment-emergent ADA-positive patients
- Number (%) of treatment-boosted ADA-positive patients
 - Number (%) of patients with neutralizing antibody

- Number (%) of patients with non-neutralizing antibody.

In addition, number (%) of patients with ADA-positive or negative response at each visit will be summarized by dose.

ADA and PK

By visit descriptive summary of serum concentration of sarilumab will be provided by ADA patient classification (positive or negative) for each dose regimen.

Scatter plots of serum concentration versus visit will also be provided by ADA classification (positive or negative) and dose regimen.

11.5 INTERIM ANALYSIS

Ongoing review of safety data will be performed by an independent DMC ([Section 6.2](#)). The timing of DMC reviews will be detailed in the DMC charter. An internal DEC will review accumulating safety, PK, PD, and efficacy data, according to the timing and rules described in [Section 6.1.2](#).

The first formal interim analysis will be performed once sufficient Week 12 data have been observed from the dose-finding portion of the study to allow a selection of a dose regimen for more detailed investigation. If the enrollments for Weight Group B are not completed within a similar time frame as that for weight Group A, the dose selection for weight Group A will be done separately from the dose selection for weight Group B, ie, two separate data analyses will be needed.

The second interim analysis will be performed approximately 1 year from the time every patient enrolled in the dose-finding and second portions has received the selected dose regimen (either new enrolled patients or patients already in the extension phase). Only patients enrolled in the dose-finding and second portions will be included in this interim analysis.

The third interim analysis will occur approximately 1 year from the time the last patient is enrolled in the third portion.

The final database lock will occur approximately 4 weeks after the last patient has completed the EOS visit.

The primary objective is PK estimation and there is no formal hypothesis testing, thus there are no statistical implications for the summary and reporting of the final data at the conclusion of the extension.

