--	--

	
renal, neurological disorders (including demyelinating disease), active infectious diseases, endocrinological, gastrointestinal, hepatobiliary, metabolic, pulmonary (eg, severe asthma, cystic fibrosis), nonmalignant lymphoproliferative diseases, other lymphatic disease(s), autoimmune disease, psychiatric disorders, etc
 
 • Patients with nonhealed/healing skin ulcers • Surgery within 4 weeks prior to the Screening visit or with planned surgery during the course of the study • History of a systemic hypersensitivity reaction, other than localized injection site reaction, to any biologic drug and known hypersensitivity to any constituent of the product • History of inflammatory bowel disease, severe diverticulitis, or previous gastrointestinal perforation whatever the cause • Uncontrolled diabetes mellitus, defined as glycosylated hemoglobin (HbA1c) $\geq 9\%$ at the Screening visit • Conditions/situations such as: 
 - Patients with short life expectancy - Conditions/concomitant diseases making patients non-evaluable for the efficacy endpoints, eg, patients with chronic pain caused by conditions other than JIA, eg, fibromyalgia - Patients whose immediate family members are dependent (employee) of site/Investigator, and individuals who are institutionalized due to regulatory or legal order. • Any of the following laboratory abnormalities at the Screening visit (identified by the central laboratory): 
 ■ [REDACTED] ■ [REDACTED] ■ [REDACTED] ■ [REDACTED] ■ [REDACTED] ■ [REDACTED] ■ [REDACTED] ■ [REDACTED] ■ [REDACTED] ■ [REDACTED] ■ [REDACTED] • Pregnant or breast-feeding female adolescent patients (refer to main body of protocol for details).
Total expected number of patients	Assuming that 3 dose regimens will be tested and one of these 3 dose regimens will be selected, up to approximately 72 patients will be enrolled (to achieve approximately 60 evaluable patients) in the dose-finding and second portions. Approximately 28 additional patients will be enrolled in the third portion to achieve a total of approximately 100 treated patients for the entire study.
Expected number of sites	Approximately 45 sites (additional sites could be opened).
STUDY TREATMENT(s)	

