6 STUDY DESIGN

6.1 DESCRIPTION OF THE PROTOCOL

DRI13925 is a multinational, multicenter, open-label, 2-phase study in children and adolescents, aged 2 to 17 years (or country specified age requirement), with pcJIA who have inadequate response to or who are intolerant to standard therapy and who will receive SC injections of sarilumab administered q2w or qw. The 2 phases are as follows:

1. A 12-week core treatment phase, split into 3 portions:

- A first sequential, ascending dose-cohort, dose-finding portion in which up to 3 dose regimens will be investigated in two weight groups: patients ≥ 30 kg and ≤ 60 kg (Group A) and patients < 30 kg and ≥ 10 kg (Group B) in 6 evaluable patients per dose and weight group (around 36 patients in total). Patient enrollment will be staggered by weight group and dose regimen, starting with Group A (≥ 30 kg and ≤ 60 kg) and Dose Regimen 1 Cohort.
- A subsequent portion where approximately 24 additional patients (12 in each weight group: ≥ 30 kg [Group A] and patients < 30 kg and ≥ 10 kg [Group B]) will be enrolled directly to the selected dose regimen (identified based on the aggregate data from patients enrolled in the dose-finding portion) to achieve a total of 18 evaluable patients per weight group at this selected dose regimen. These patients will undergo the same 12-week core treatment assessments as patients recruited during the dose-finding portion.
- A third portion where approximately 28 additional patients (a cap of 70% in each weight group: patients ≥ 30 kg [Group A] and patients < 30 kg and ≥ 10 kg [Group B]) will be enrolled directly to the selected dose regimen to achieve a total of approximately 100 treated patients for the entire study. These patients will undergo the same on-site visits during the 12-week core treatment phase as patients recruited in the dose-finding and second portions; however, the patients in the third portion will not have the sarilumab PK sampling visits between Baseline and Week 2.

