6.1.2.4 Rules for dose regimen selection

The decision about the selected dose regimen will be made by the DEC after review of sufficient Week 12 PK, PD, efficacy, and safety data from the patients enrolled in the dose-finding portion of the study.

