8.4 METHOD OF ASSIGNING PATIENTS TO TREATMENT GROUP

The list of randomized treatment kit numbers will be generated centrally by Sanofi. The IMPs are packaged in accordance with this list. Patients will be assigned a treatment kit by an interactive voice response system (IVRS) or an interactive web response system (IWRS).

Patients who meet the entry criteria will be included and will be dispensed the treatment kits within 2 weight groups (Group A: ≥ 30 kg and ≤ 60 kg for patients enrolled during the dose-finding portion and ≥ 30 kg for patients enrolled during the second and the third portions; Group B: < 30 kg and ≥ 10 kg for all 3 portions).

- For the dose-finding and second portions, the planned ratio of enrollments for the 2 weight groups is 1:1.
- For the third portion, there is no pre-specified enrollment ratio for the 2 weight groups, but each weight group will be capped at 70% (ie, 20 patients). As a result, the most unbalanced enrollments by weight group possible would be 20 versus 8 patients in the third portion.

Patients who meet exclusion criteria may be rescreened once during the open screening period of the study. A different patient identification will be issued. There is no requirement for a waiting period between the screen failure and the rescreening. The IVRS/IWRS report will flag rescreened patients. Patients that are rescreened will be required to sign a new consent form (if the patient has reached the legal age) or by parents or legal guardians. Visit 1 procedures must be repeated (except chest X-ray).

At the Screening Visit 1 (Day-28 to D-1, up to 31 days), the site staff will contact the IVRS/IWRS to obtain a patient number for each patient who gives informed consent. Each patient will be allocated a patient number associated with the center and allocated in chronological order in each site.

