### 2.4.6.1 Analysis of JIA ACR30 response

Patients achieving JIA ACR30 [REDACTED] response for each dose regimen cohort, overall and by weight group, will be summarized by visit using counts, proportions and 95% CIs. The primary approach will be based on all observed data while the patient remains on treatment. No missing data will be imputed.

Additionally, for the summaries on the JIA ACR30 responses during the 12-week core treatment part, several different approaches will be used for the handling of treatment discontinuations and missing data.

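### The absence of hypothesis testing does not remove selection bias: the selected regimen's pooled ACR rates may read a few points high, to the extent that efficacy drives the choice (minor)

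*Protocol*

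**What the plan says.** **How the regimen is chosen.** Protocol 6.1.2.4 has the DEC decide "after review of sufficient Week 12 PK, PD, efficacy, and safety data from the patients enrolled in the dose-finding portion". The visible text gives no numerical rule and no weight for efficacy. Under 11.5, the two weight groups may be decided separately. The synopsis allows the choice to be an intermediate regimen that was not one of the three tested.

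**Who is counted.** Dose-finding studies each regimen "in 6 evaluable patients per dose and weight group (around 36 patients in total"). About 12 more patients per weight group then join at the selected regimen "to achieve a total of 18 evaluable patients per weight group at this selected dose regimen". The third portion adds about 28 at that regimen. The efficacy population (protocol 11.3.1, SAP 2.3.3) is everyone dosed, whichever portion they entered.

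**What is reported.** SAP 2.4.6.1 states that ACR30 "response for each dose regimen cohort, overall and by weight group, will be summarized by visit using counts, proportions and 95% CIs". SAP 2.4.6.2 applies the same methods to ACR50/70/90/100 and gives means with 95% CIs for the core-set variables. SAP 2.4.6 keeps data after a dose adjustment separate. No further efficacy subgroup summaries are planned.

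**What is concluded.** Protocol 11.5 and SAP 3 reason from PK estimation and the lack of testing that, at the end of the extension, "there are no statistical implications for the summary and reporting of the final data".

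**The concern.** The inference is wrong for an estimate. Without tests there is no type I error to inflate. But when a cohort is picked partly because its observed response was high, and that same response is then counted in the reported rate, the estimate carries part of the chance excess that helped it win. The regimens not picked carry the matching deficit. Neither effect depends on a p-value being computed.

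Descriptive rates and CIs are the trial's only efficacy output. At stake are the accuracy of the selected regimen's ACR rates and the apparent gap between regimens when they are shown side by side.

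**Working it through.** **1. The plan's own counts reproduce.**
- Dose-finding: 3 regimens × 2 weight groups × 6 = 36.
- Selected regimen: 6 + 12 = 18 per weight group.
- First two portions: 36 + 24 = 60 evaluable. The synopsis has "up to approximately 72 patients will be enrolled (to achieve approximately 60 evaluable patients) in the dose-finding and second portions", and 72 + 28 = 100 treated.
- Third portion: 0.70 × 28 = 19.6, in line with protocol 8.4, where "each weight group will be capped at 70% (ie, 20 patients"). The split lies between 14/14 and 20/8.
- Selected regimen, both weight groups, at the end: 12 + 24 + 28 = 64.

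The documents give no bias or coverage figure to reproduce.

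**2. Assumptions not in the documents.** The three regimens have equal true ACR30 rates p between 0.5 and 0.9. In the limiting case the regimen with the highest observed rate is chosen, with ties broken at random.

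**3. Formula.** With n1 dose-finding patients per regimen and F the Binomial(n1, p) distribution function, the expected best count of three is n1 − Σ F(x)³ over x = 0 to n1 − 1. The excess in the chosen cohort is that count divided by n1, minus p. The pooled bias is (n1/N) × excess.

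Example, p = 0.7, n1 = 6: F(2) to F(5) are 0.0705, 0.2557, 0.5798 and 0.8824, and smaller terms are negligible. The sum of cubes is 0.899, so the expected best count is 5.101 and the rate is 0.850. The excess is 15.0 points. Pooled to 18 it is 15.0 × 6/18 = 5.0 points.

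**4. Limiting case (ACR30 alone decides), bias in points.**

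| True rate | Excess in chosen 6 | N=18 | N=32 | Excess in chosen 12 | N=36 | N=64 |
|---|---|---|---|---|---|---|
| 0.5 | 16.9 | 5.6 | 3.2 | 12.1 | 4.0 | 2.3 |
| 0.7 | 15.0 | 5.0 | 2.8 | 10.9 | 3.6 | 2.0 |
| 0.8 | 12.6 | 4.2 | 2.4 | 9.3 | 3.1 | 1.7 |
| 0.9 | 8.3 | 2.8 | 1.6 | 6.6 | 2.2 | 1.2 |

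N=18 and N=32 are per weight group with separate selection. N=32 takes an even third-portion split; the permitted range is 26 to 38. N=36 and N=64 are both groups with one selection. With unequal true rates of 0.7/0.8/0.9 the bias falls to 3.3 (N=18), 2.0 (N=36) and 1.1 (N=64).

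**5. Non-selected regimens.** With equal true rates the three cohort errors average zero, so each non-selected regimen is low by half the excess: 16.9/2 = 8.5 points at p = 0.5 and 8.3/2 = 4.1 at p = 0.9 with 6 per regimen.

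**6. Efficacy as part of the choice.** Let the selection score be one quarter response and three quarters unrelated information, by variance. The score's correlation with response is √0.25 = 0.5, so the bias roughly halves. Simulation at p = 0.5 to 0.85 gives 1.9-2.9 points at N=18, 1.4-2.1 at N=36 and 0.8-1.2 at N=64. At zero weight the bias is zero.

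**7. Against the interval.** Clopper-Pearson half-widths are about 21 points for 14/18 and 10.5 for 51/64. In the limiting case at N=18 and p = 0.8, Clopper-Pearson coverage moves from 96.6% to 95.6%, and the chance that the lower limit exceeds the truth rises from 1.8% to 4.1%. The visible SAP names no interval method. The Wald interval, at 88.5% without selection in that setting, falls to 80.8%.

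**The case against.** The strongest case against is that the documents never show efficacy deciding the regimen. The primary objective is to use the PK profile to identify the dose, the regimens are defined by adult exposure targets, and the DEC weighs four kinds of data. Safety could even favour a regimen with lower observed response. Efficacy is secondary and descriptive, no threshold depends on an ACR rate, and protocol 4.3.2 justifies 18 per weight group by precision for PK and PK-PD. All of this stands. It limits the size of the problem but does not repair the inference.

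A reader might infer that the selected regimen's rates are certainly too high and that the tables will necessarily favour it. The documents do not support that. No selection rule is visible, the direction is only the expected one if chance response influenced the choice, and under an intermediate regimen no dose-finding child received the selected regimen in the core phase.

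A reader might also infer that the post-selection rate should replace the pooled rate as the quoted result. That does not follow either. It discards a third of the 18. The second and third portions also admit patients over 60 kg, whom exclusion criterion E 01 kept out of dose-finding, so the two columns do not describe quite the same population. A descriptive plan has no headline efficacy estimate to reassign.

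Finally, SAP 2.4.11 and the Appendix C mock-up tables are not visible, so an existing by-portion table cannot be excluded. Their titles concern dose adjustment rather than enrolment portion.

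**Conclusion.** The point holds in a limited form and is minor. The absence of testing supports a statement about type I error only. The pooled ACR rates of the selected regimen may be biased upward, and those of the other regimens downward, to the extent that efficacy drives the selection.

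The upper bound on the pooled bias is about 3-6 points at n=18 per weight group and 1-2 points at n=64. It rests on assumed equal true response of 50-90% and selection on ACR30 alone. A quarter weight brings it to about 2-3 points and 1 point. It is zero if PK alone decides and is unrelated to chance response, or if an intermediate regimen is chosen. Every figure is well inside the CI half-width. The effect on a Clopper-Pearson interval is mainly one-sided, with little loss of total coverage, so a reading that the intervals fail badly because of selection is not supported.

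**What to change.** 1. In protocol 11.5 and SAP 3, limit the sentence to type I error. Add that pooled efficacy estimates for the selected regimen that include the dose-finding cohorts may carry selection bias, because Week 12 efficacy of those cohorts contributes to the choice.
2. In SAP 2.4.6.1 and 2.4.6.2, keep the pooled summary. Add a supportive column for core-phase ACR responses, core-set changes and JADAS-27 at the selected regimen in patients enrolled after selection (second and third portions). Note beside it that these portions also admit patients over 60 kg. This column has no selection bias by construction.
3. Label any side-by-side display of regimens from the dose-finding cohorts as the data used for selection.

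The cost is SAP wording and one table column, with no new data. The added column has a wider CI: 12 against 18 per weight group gives √(18/12) = 1.22, about 22% wider, and 52 against 64 overall gives √(64/52) = 1.11, about 11% wider. At a true rate of 0.8, normal-approximation half-widths go from 18.5 to 22.6 points and from 9.8 to 10.9 points. If the unseen sections already contain a by-portion table, only items 1 and 3 remain.

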12 ETHICAL AND REGULATORY CONSIDERATIONS

12.1 ETHICAL AND REGULATORY STANDARDS

This clinical trial will be conducted by the Sponsor, the Investigator, delegated Investigator staff and Sub-investigator, in accordance with the principles laid down by the 18th World Medical Assembly (Helsinki, 1964) and all applicable amendments laid down by the World Medical Assemblies, in particular the Declaration of Helsinki as amended in 1996 for clinical trials with medicinal products in the EU, and the ICH guidelines for good clinical practice (GCP), all applicable laws, rules and regulations.

This clinical trial will be conducted by the Sponsor, the Investigator, delegated Investigator staff and Sub-investigator, in accordance with the principles laid down by the 18th World Medical Assembly (Helsinki, 1964) and all applicable amendments laid down by the World Medical Assemblies, and the ICH guidelines for GCP, all applicable laws, rules and regulations. This clinical trial will be recorded in a free, publicly accessible, internet-based registry, no later than 21 days after the first patient enrollment, in compliance with applicable regulatory requirements and with Sanofi public disclosure commitments.

12.2 INFORMED CONSENT

The Investigator (according to applicable regulatory requirements), or a person designated by the Investigator, and under the Investigator's responsibility, should fully inform the patient who is ≥ 6 years and parent(s) or legal guardian(s) of all pertinent aspects of the clinical trial including the written information giving approval/favorable opinion by the Ethics Committee (IRB/IEC). All patient(s)/parent(s)/legal guardian(s) should be informed to the fullest extent possible about the study, in language and terms they are able to understand.

It is the responsibility of the Investigator or designee (if acceptable by local regulations) to obtain written informed assent from each patient ≥ 6 years of age (or above an age determined by the IRB/IEC and in accordance with the local regulations and requirements) and written informed consent from each patient's parent(s) or legal guardian(s) prior to the patient's participation in the study. The written informed consent should be signed and dated by the patient's parent(s) or legal guardian(s) and the same Investigator or designee.

Local law must be observed in deciding whether 1 or both parents/guardians consent is required. If only 1 parent or guardian signs the consent form, the Investigator must document the reason the other parent or guardian did not sign. The patient may also be required to sign and date the ICF as determined by the IRB/IEC and in accordance with the local regulations and requirements.

- Patient(s)/parent or legal guardian(s) who can write but cannot read will have the assent/consent form read to them before writing their name on the form

- Patients/parent or legal guardian who can understand but who can either write nor read will have the informed assent/consent form read to them in presence of an impartial witness, who will sign and date the assent/consent form to confirm that informed consent was given.

The original assent/consent form must be retained by the Investigator as part of the patient's study record and a copy of the signed assent/consent form must be given to the patient/patient's parent(s) or legal guardian(s).

The patient's general practitioner (family doctor) if any and if the parents/legal guardian and patient agree will be informed by the Investigator of the patient's participation in this study. Information regarding the study treatment will be sent to the family doctor.

The informed assent/consent form used by the Investigator must be reviewed and approved by the Sponsor prior to submission to the appropriate Ethics Committee (IRB/IEC) for approval/favorable opinion. In relation with the population of patients exposed in the trial, ie, pediatric/minor patients, the IRB/IEC should ensure proper advice from specialists with pediatrics expertise (competent in the area of clinical, ethical, and psychosocial problems in the field of pediatrics) according to national regulations. A copy of the IRB/IEC-approved assent/consent form and documentation of approval must be provided to sponsor before initiation of the study.

In relation with the population of patients exposed in the trial, ie, pediatric/minor patients, the IRB/IEC should ensure proper advice from specialists with pediatrics expertise (competent in the area of clinical, ethical, and psychosocial problems in the field of pediatrics) according to national regulations.

If new safety information results in significant changes in the risk/benefit assessment, the ICF must be reviewed and updated appropriately. All study patients and their parents or legal guardian(s) must be informed of the new information and provide their written assent (if applicable) or consent if they wish the patient to continue in the study. The original signed revised assent/consent form must be maintained in the patient's study record and a copy must be given to the patient's parent(s) or legal guardian(s). If the race/ethnic origin of the patients will be collected in the clinical trial, the scientific justification should be specified in [Section 14.5](#).

A locally approved specific consent form will be signed by patients who require Gilbert syndrome genetic testing (consent must be obtained prior to performing this assessment and local regulations should be respected).

